8.3.3 Subgroup Analyses

An analysis will be performed to evaluate whether any significantly different effects exist in the primary endpoints within subgroups of subjects. The list of covariates (with applicable subgroups in parentheses) will include at least the following:

⁹ Additional data analysis and reporting may be performed after a sub-set of subjects have completed their Assessment for regulatory submission outside of the United States.

- Subject demographics (e.g., age-[e.g. age >=65 vs. <65, Medicare eligible], gender)
- Subject baseline characteristics (e.g., LVEF, cardioversion history, BMI, and LA diameter)
- Index Procedure lesion sets
 - PV + LAPW ablation alone versus PV + LAPW plus additional ablations
 - CTI ablation versus no CTI ablation
- Geography
- FARAPULSE PFA System used (Investigational vs. Commercial)

Each subgroup covariate will be included as a single independent variable in a logistic regression model with the primary endpoint outcome as the dependent variable and a test for significance at the 15% level will be performed.

In addition to subgroup analyses, descriptive statistics of subject demographic and baseline characteristics will be presented for each subgroup listed in this section.

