8.1.1.3 Statistical Methods

The proportion of Treatment Subjects and Attempt Subjects with one or more CSAEs will be estimated using the Kaplan-Meier method. The 97.5% one-sided upper confidence limit of the observed event rate will be compared to the performance goal of 12%. If the upper confidence limit is less than the performance goal, the null hypothesis will be rejected. The upper confidence limit will be calculated as the pointwise confidence limit using the log-log methodology.

Subjects who withdraw from the study prior to the Day 90 Assessment without experiencing a primary endpoint event will be censored on the date of withdrawal. Subjects who undergo a re-ablation procedure using a commercially available ablation catheter before the Day 90 Assessment without experiencing a primary endpoint event will be censored as of the date of that re-ablation procedure. Subjects who are determined to be Severe COVID-19 Subjects during trial participation without experiencing a primary endpoint event will be censored as of the Onset Date of the condition.

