8.1.2.3 Statistical Methods

The proportion of LUX-Dx monitored Treatment Subjects with PersAF Treatment Success through the Day 360 Assessment will be estimated using the Kaplan Meier method. The 97.5% one-sided lower confidence limit of the observed Treatment Success rate will be compared to the performance goal of 40%. If the lower confidence limit is greater than the performance goal, the null hypothesis will be rejected. The confidence limit will be calculated as the pointwise confidence limit using log-log methodology.

Each LUX-Dx monitored Treatment subject will be classified as Treatment Success (event-free) or Treatment Failure (PEE event). Subjects must have an active LUX-Dx device with established LATITUDE Clarity connection by the end of the effectiveness evaluation period to be included in PEE analysis. Subjects who withdraw or die from the study prior to the Day 360 Assessment, without experiencing a PEE event, will be censored on the date of withdrawal or death. Subjects who are determined to be Severe COVID-19 Subjects during trial participation without experiencing a PEE event will be censored as of the Onset Date of the condition.

LUX-Dx data will be used to simulate intermittent arrhythmia monitoring methods consistent with the methods used in ADVANTAGE AF Phase 1. Bi-monthly (asymptomatic) event monitor transmissions will be simulated by randomly selecting LUX-Dx data from two, 2-minute time windows every 30 days starting on the date of the Day 90 assessment. Each 30-day interval contains 2,592,000 seconds from which 2 seconds will be selected via simple random sampling and used as the starting point for a 2-minute (120 second) window. The first 2-minute window will be removed prior to sampling the second 2-minute window to avoid overlapping windows. The sampling seed will equal the date of the first subject enrollment..

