8.3.4 Subgroup Analyses

Analyses will be performed to evaluate whether any significantly different effects exist in the Primary Safety Endpoint or Primary Effectiveness Endpoint within subgroups of subjects. The list of covariates (with applicable subgroups in parentheses) will include at least the following:

- Subject demographics (e.g., age-[e.g. age >=65 vs. <65, Medicare eligible], gender)
- Subject baseline characteristics (e.g., LVEF, cardioversion history, BMI, LA diameter, and years since AF diagnosis)
- Index Procedure lesion sets
 - PV + LAPW ablation alone versus PV + LAPW plus additional ablations
 - CTI ablation versus no CTI ablation
- Operator learning curve (e.g. number of prior procedures completed by operator at time of procedure, counting at a minimum, the procedures from ADVANTAGE AF Phase 1 and Phase 2)
- Mapping of the PW during Index Procedure

Additional covariates for the Primary Effectiveness Endpoint only include:

- Amiodarone use post Index Procedure versus no Amiodarone use post Index Procedure.
- LUX-Dx model (LUX-Dx II+ [M312] vs LUX-Dx [M301] or LUX-Dx II [M302])

Each subgroup covariate will be included as a single independent variable in a logistic regression model with the endpoint outcome as the dependent variable and a test for significance at the 15% level will be performed.

In addition to subgroup analyses, descriptive statistics of subject demographic and baseline characteristics will be presented for each subgroup listed in this section.

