8.3.7 Multivariable Analyses

For the Primary Safety Endpoint and Primary Effectiveness Endpoint, univariable analyses of the following covariates will be performed, and any found to be significantly associated with the outcome at the 0.15 alpha level will be included as covariates in a multivariable regression model. Backward selection with 0.15 alpha level stay criterion will be used to determine the final multivariable model.

The list of baseline covariates includes, but is not necessarily limited to:

- Subject demographics (e.g., age, gender)
- Subject baseline characteristics (e.g., LVEF, cardioversion history, BMI, LA diameter, and years since AF diagnosis)
- Index Procedure lesion sets
 - PVI + LAPW ablation alone versus PVI + LAPW plus additional ablations
 - CTI ablation versus no CTI ablation
- Operator learning curve (e.g., number of prior procedures completed by operator at time of procedure, counting at a minimum, the procedures from ADVANTAGE AF Phase 1 and Phase 2)
- Mapping of the PW during Index Procedure

Additional covariates for the Primary Effectiveness Endpoint only include:

- Amiodarone use post Index Procedure versus no Amiodarone use post Index Procedure
- LUX-Dx model (LUX-Dx II+ [M312] vs LUX-Dx [M301] or LUX-Dx II [M302])

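### Subgroup tests use logistic regression on endpoints that the primary analysis censors, and the plan does not say how censored subjects enter the model

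*Combined protocol and SAP*

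**What the plan says.** **Subgroup tests.** Appendix A Section 8.3.4 (Phase 2) prescribes one model per covariate: "Each subgroup covariate will be included as a single independent variable in a logistic regression model with the endpoint outcome as the dependent variable". It adds that "a test for significance at the 15% level will be performed". Phase 1 Section 8.3.3 is the same in substance: "Each subgroup covariate will be included as a single independent variable in a logistic regression model". Both apply to the primary safety endpoint (PSE) and the primary effectiveness endpoint (PEE).

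**Primary analyses.** For the PSE (Section 8.1.1.3 in both phases), "The proportion of Treatment Subjects and Attempt Subjects with one or more CSAEs will be estimated using the Kaplan-Meier method". A subject who withdraws "without experiencing a primary endpoint event will be censored on the date of withdrawal". Severe COVID-19 and certain re-ablations also censor. For the PEE (Section 8.1.2.3 in both phases), the success proportion "will be estimated using the Kaplan Meier method" in Phase 2 and likewise in Phase 1, with censoring at withdrawal, death or onset of severe COVID-19.

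**Binary rule.** The PEE methods paragraph also sorts each Treatment Subject into success, meaning event-free, or failure, meaning an endpoint event. It does not say whether that sorting governs the logistic model.

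**Multivariable analysis.** Appendix A Section 8.3.7 (Phase 1 Section 8.3.5) runs its own univariable analyses, and "any found to be significantly associated with the outcome at the 0.15 alpha level will be included as covariates in a multivariable regression model". The type of regression is not stated.

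**The concern.** A logistic model needs a yes or no for every subject. Someone who leaves event-free at Day 150 has neither for a Day 360 endpoint, and must be called a success, called a failure, imputed or removed. The documents choose none of these. The literal PEE sorting would make that subject a success, while the same paragraph censors the subject.

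The choice matters when dropout differs by subgroup. If leavers count as successes, the subgroup with more leavers looks better. If they are removed, it looks worse, because early failures stay in while event-free leavers go out. Either way the test partly measures retention. Age 65 or older is one of the listed covariates, and dropout or death could plausibly differ there. A difference may be flagged or missed for reasons unrelated to the device.

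**Working it through.** **1. The plan's own figures.** No figure is given for the subgroup tests, so the check starts from the primary sample sizes (exact binomial, one-sided 0.025).

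- PEE, n = 122, 55% vs 40%: reject at 60 or more successes; alpha 0.0248, power 91.6% (stated 90%). 122/0.90 = 135.6, so 136.
- PSE Phase 2, n = 245, 6% vs 12%: reject at 19 or fewer events; alpha 0.0211, power 89.8% (stated 88%). 245/0.95 = 257.9, so 258.
- PSE Phase 1, n = 232: power 89.4% at that exact n (stated 86%). The lowest power for any n of 232 or more is 86.2%, which matches the stated figure.

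**2. Inputs for the subgroup check.** From the documents: true PEE success 55%, attrition 10% per year, 258 Treatment Subjects, test level 15%. Assumed: two equal subgroups of 129, 3% acute failure at Day 0, constant failure hazard after Day 90, exponential non-informative dropout, and the subgroup-specific dropout rates.

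**3. Apparent PEE failure rate at 10% dropout.** Let h be the failure hazard after Day 90 and k the dropout hazard.

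- h = ln(0.97/0.55)/270 = 0.002101 per day
- k = -ln(0.90)/360 = 0.000293 per day
- Observed failures = 0.03 + 0.97 × 0.90^0.25 × h/(h+k) × (1 − exp(−270(h+k))) = 0.425
- Complete and event-free = 0.55 × 0.90 = 0.495
- Censored event-free = 1 − 0.425 − 0.495 = 0.080, or about 21 of 258

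Scored as successes, the failure rate is 42.5% instead of 45%. With these subjects excluded it is 0.425/(0.425 + 0.495) = 46.2%. Kaplan-Meier targets 45%.

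**4. Rejection rate at the nominal 15% level, no true subgroup difference (PEE).** Ranges span separate simulation runs. With 4,000 trials one standard error is √(0.15 × 0.85/4000) = 0.6 points.

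| Dropout in the two subgroups | Logistic, dropouts = success | Logistic, dropouts excluded |
|---|---|---|
| 10% / 10% | 14.1-14.9% | 14.6-15.8% |
| 5% / 15% | 17.8-19.0% | 15.1-15.9% |
| 3% / 20% | 24.5-27.3% | 17.2-19.0% |
| 0% / 20% | 27.7% | 18.9% |

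Log-rank stayed between 14.3% and 15.6% across these settings.

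**5. Power with a real difference (true success 48% vs 62%).**

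| Dropout (48% group / 62% group) | Log-rank | Dropouts = success | Excluded |
|---|---|---|---|
| 10% / 10% | 78.2% | 76.8% | 78.0% |
| 5% / 15% | 76.5% | 86.6% | 70.3% |
| 15% / 5% | 77.5% | 62.5% | 82.6% |

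With unequal dropout the logistic result moves in opposite directions depending on the coding. Log-rank hardly moves.

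**6. PSE.** With a true rate of 6% and events assumed to fall within 30 days, 5% attrition by Day 90 gives 5.95% (leavers scored event-free) or 6.25% (excluded). With 10% by Day 360 the figures are 5.98% or 6.60%. Appendix A Section 8.1.1 supports the early timing: all events in its meta-analysis began within 30 days.

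**The case against.** The strongest reply is that this is a small gap in secondary analyses. Most of its parts stand.

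- **Study success rests on the two primary tests only** (Appendix A Section 8.2.3). True.
- **At equal dropout nothing happens to the test level.** True. The inflation needs differential dropout, and the documents give no subgroup-specific rates.
- **The consequence is small against the screen's own noise.** Section 8.3.4 names at least 13 PEE covariates, so 13 × 0.15, about two, will be flagged by chance. Moving one test from 15% to 18.5% adds 0.035 of a flag.
- **A separate SAP may define the coding.** Possible. Neighbouring sections refer to it and it was not available. Section 8.3.4 itself does not defer to it.
- **A binary model suits a fixed-horizon proportion, and Cox regression assumes proportional hazards.** The PEE has acute failures, a blanking period and detection around visits, so Cox is not ideal. But log-rank, or a Kaplan-Meier comparison at Day 360, needs no such assumption for a valid test.

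A reader might also infer more than the text supports:

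- That the plan scores withdrawals as successes or drops them. It says neither; counting them as failures or imputing them is equally open.
- That the 15% subgroup test selects covariates for the multivariable model. Phase 1 Section 8.3.5 and Appendix A Section 8.3.7 describe their own univariable step, and nothing identifies it with the logistic test.
- That reported subgroup rates must disagree with the primary rate. The subgroup sections do not say that rates will come from the logistic model.
- That death is censored for both endpoints. It is a listed censoring reason only for the PEE; related death is a PSE component.

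**Conclusion.** The point holds as a minor one. The prescribed model cannot represent the censoring that the primary analyses use, and the available documents do not say how censored subjects are coded.

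The effect is essentially confined to the PEE. Equal 10% dropout leaves the level near 15% and shifts the apparent failure rate by about 2.5 points if leavers count as successes. Under assumed dropout of 5% vs 15%, a true null is rejected about 18-19% of the time (leavers as successes) or 15-16% (excluded). At 3% vs 20% the figures are about 24-27% and 17-19%. These results rest on equal subgroups, non-informative dropout within each subgroup, and dropout differences that are illustrations, not figures from the plan. Dropout that is informative within a subgroup would affect log-rank as well.

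Nothing here touches the primary tests or the sample size.

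**What to change.** In Appendix A Section 8.3.4 and Phase 1 Section 8.3.3, replace logistic regression for the PEE, and for consistency the PSE, with a log-rank test or Cox regression under the censoring rules of Sections 8.1.1.3 and 8.1.2.3. Cox is the natural choice for covariates kept continuous, such as operator experience. Report Kaplan-Meier rates with log-log limits by subgroup. Keep Day 0 acute procedural failures as events, for example by giving them a small positive time so that software does not discard them. State the same type of model for the multivariable analyses (Phase 1 Section 8.3.5, Appendix A Section 8.3.7).

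If logistic regression is kept, state how each kind of censored subject is coded and add a sensitivity analysis under the opposite coding. The chi-square poolability tests (Phase 1 Section 8.3.4, Appendix A Section 8.3.5) need the same sentence.

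The cost is SAP wording and programming. The one downside is the proportional-hazards assumption if Cox is used. No power is lost at equal dropout (78.2% for log-rank against 76.8% and 78.0% for logistic).

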8.3.5 Center Pooling Analysis

Center-to-center heterogeneity will be assessed for the primary endpoints. Descriptive statistics for each primary endpoint will be presented by site and heterogeneity will be tested with a Chi-square test, treating site as a fixed effect. If sites are not deemed poolable in the initial Chi-square analysis, poolability analysis will be reperformed by treating site as a random effect. A significance level of 15% will be used for each test. Sites with less than five Non Roll-in Treatment and Attempt subjects will be excluded from statistical tests for heterogeneity on the Primary Safety Endpoint, and sites with less than five Non Roll-in, LUX-Dx monitored Treatment subjects will be excluded from tests for heterogeneity on the Primary Effectiveness Endpoint.

8.3.6 Treatment Success Rate by Arrhythmia Detection Method

PersAF Treatment Success rates through Day 360 Assessment will be compared between ADVANTAGE AF Phase 1 and Phase 2 Treatment Subjects to assess differences in chronic success when using the continuous monitoring from an ICM to simulate non-continuous monitoring for recurrence compared to standard assessment based on true Holter monitoring and periodic

transmissions from event monitors. A propensity score analysis utilizing inverse probability of treatment weights (IPTW) will be used to estimate the absolute difference in PersAF Treatment Success rates between detection groups (ICM vs. Standard) while minimizing the effects of confounding variables. Details of this analysis will be included in the Appendix A of the ADVANTAGE AF SAP.

